5.2 Study treatment

5.2.1 Description

The surgical technique of LSGG is described in detail in appendix 2. Furthermore, a video of the technique will be made avaliable.

5.2.2 Justification comparator

The comparator will be LSG performed in the same way without gastropexy.

5.2.3 Concomitant therapy

Crural repair for all patients with a Hill grade IV, and for Hill grade III if judged necessary by the operating surgeon and in accordance with the first international consensus conference on reflux and LSG.¹⁷ The repair should be performed to such an extent that the diaphragmatic crura comes close to the oesophageal wall. Crural repair is shown in the illustrating video.

6 RISKS AND BENEFITS

Complications that might appear are assumed to be similar to what is already known for the LSG.

6.1 Anticipated clinical benefits

The anticipated benefit will be reduced incidence of GORD. If so, for the individual patient this should have the potential to improve HRQL and reduce the need for ARM and reoperation due to GORD. On a societal level this could reduce costs for ARM and possibly reduce the necessity for postoperative surveillance.

6.2 Anticipated adverse events

Leaks, excess bleeding, and unintentional kinking/torsion/stricture of the gastric remnant could be potential adverse events. However, no increase in such events have been found in the few studies published on this technique.

6.3 Possible interactions with concomitant treatments

A crural repair is recommended in conjunction with LSG if the hiatus is enlarged.¹⁷ Although this is recommended by experts through consensus statements, it is per as today not always performed. In this study it will be standard to perform crural repair if indicated (see 5.2.3), independent of what group the patients is allocated to. A crural repair by itself might influence GORD, but since it will be performed on the same indications in both groups, the specific influence of gastropexy can be studied independently of whether crural repair have been done or not.

6.4 Steps to be taken to control or mitigate risks

A video illustrating the surgical technique of gastropexy and crural repair will be available. Surgical teams who wish to participate in the study must record a video illustrating the performance of the LSGG. This video will be presented to the TSC who will evaluate the performance and decide whether to allow entrance to the study or not.

Version no 4.0 RESEARCH PROTOCOL Clinical intervention study

6.5 Subjects

6.5.1 Inclusion criteria

Inclusion criteria will be based on guidelines for bariatric surgery as stated by IFSO/ASMBS:18

• BMI ≥ 35

6.5.2 Exclusion criteria

The following must not be present at the time of enrolment:

- Age below 18 years
- Previous bariatric surgery
- Previous antireflux surgery
- Use of acid-reducing medication (ARM) for other reasons than reflux
- Inability to comprehend and respond to the PRO questionnaire
- LSG planned as the first step of a Biliopancreatic Diversion with Duodenal Switch (BPDDS).

6.5.3 Criteria for withdrawal or discontinuation

Subjects can withdraw from the clinical study at any time without any rationale, and without compromising their future medical care. Patients may withdraw from the PRO-part, but still be included in the rest of the study procedures. Patients who are withdrawn from the study will be followed according to standard care.

6.5.4 Enrolment

Patients with obesity who qualifies for bariatric surgery (see 6.5.1) and are being planned for LSG are candidates for enrolment in this clinical study. Following review of the inclusion and exclusion criteria, eligible subjects will be invited to participate in this clinical study. Information on the study, the fact that it involves research, the purpose of the clinical study, potential risks/benefits and the necessity of including individual information on height, weight, diseases, use of medication, smoking and findings at gastroscopy will be given to the subject.

All subjects must give written informed consent prior to participation. Once the subject has given written informed consent, they can be enrolled into the clinical study.

Hospitals might differ in regard to selection criteria for offering LSG, and also how the LSG is performed. This study is not intended to influence on the individual hospital selection criteria, but when a patient is included in this study, the protocol should be followed.

The subject's participation in this clinical study is completely voluntary. If the subject decides not to participate in the clinical study, their decision will have no impact on any services or treatment the subject are currently receiving, and will also not affect their relationship with their caregivers. Subjects are allowed to withdraw their participation at any time during the course of the study without sacrificing their rights as a patient or compromising their quality of medical care.

6.5.5 Duration of the clinical study

The duration of the study will partly be dependent on the number of participating hospitals, partly on the number of LSG's performed within these hospitals, and partly on the patients willingness to participate. The date of operation for the first included patient represent the

	RESEARCH PROTOCOL
Version no 4.0	Clinical intervention study

study start date, and the final follow-up is five years after the day of operation of the last patient. We estimate an inclusion period of two years, hence the maximum time from inclusion to last patient visit will ideally be four years for the two-year data, and seven years for the five-year data. Allowing six months for delayed follow-ups, and six months for data processing/cleaning, the total duration for the clinical study will be eight years. See figure 1 (chapter 3.3) for time-schedule of the project.

6.5.6 Expected subject duration

The treatment period for the individual patient will be five years.

6.5.7 Number of subjects

A total of 900 patients will be randomized, see chapter 7.2.

6.5.8 Time to select all subjects

The study will remain open for enrolment until the planned number of subjects is randomized (n=900), estimated to approximately two years.

6.6 Procedures

6.6.1 Clinical study procedures

At the screening visit the following tests and examination will be carried out to screen eligible subjects and provide baseline information for those patients that meet the study criteria:

- History and physical examination including height, weight and blood pressure.
- Laboratory tests.
- Gastroscopy, pH-metry and impedance measurements in a subgroup of patients (n=30).

All tests must be completed not more than six months prior to undergoing the LSG unless otherwise stated.

PRO-questionaires and the GerdQ will be answered by the patients preoperatively and at one, two and five years.

Follow-up: The time point for follow-up will be six weeks, and one, two and five years after the operation. The six-week follow-up will focus on complications. At the one, two and five year follow-up, clinical, biochemical and PRO-data including GerdQ will be collected. Gastroscopy and pH-metry will be performed two years after the operation, and the findings will be reported using the same standardized form as the preoperative gastroscopy (appendix 1).

6.6.2 Activities performed by representatives for research responsible institution and participating hospitals

The research responsible institution will have the main responsibility for the study. This includes writing and revising the research protocol, EC application with attachments, site documentation (video documentation) from each hospital before entry to the study, distributing envelopes with codes for participating surgeons, distributing sealed envelopes for randomization, receiving and storing the data in a secure database, data management and statistics. Surveillance and management of adverse events will be performed in cooperation with the TSC.

	RESEARCH PROTOCOL
Version no 4.0	Clinical intervention study

One representative for each participating country will be responsible for writing an EC application applicable for his or her country.

Each participating hospital will point out one person to coordinate the study within that hospital. This includes patient recruitment, obtaining written informed consent, local data management, correspondence with the national coordinator and with the Project Leader / institution responsible for this study. All included patients will be given a unique patient ID number. This number is the ID that is generated automatically by SOReg. All included patients in Sweden will thus have a six digits code number and all included patients in Norway will have a five digits code number. An updated list of included patients with overview of group allocation must be kept in a safe place within the hospital. A copy of this list containing the patient ID (no name or other identifiable data) shall be sent to SOReg-N on the first day of every month (see also 5.1.5 and 5.1.6 and appendix 17.6). Hospitals participating in the Bravo-arm of the study must balance the number of patients themselves so that an equal number of patients are allocated to the pexy and no-pexy group, respectively.

6.6.3 Factors that may compromise the outcome of the clinical study / interpretation of the results

This study is a randomized trial where the patients will be randomized into two groups. Potential differences between the groups like age, preoperative use of ARM and smoking will be accounted for by statistical methods.

Potential differences in performance between surgeons will be explored and adjusted for by statistical methods if found.

Missing values at two years will be accounted for by multiple imputation as necessary. Missing value at baseline will exclude the patient from the study.

Potential differences in culture and tradition between hospitals and countries for prescribing ARM, and similarly potential differences among patients demand for having ARM will be sought overcome by standardizing the information: ARM used in conjunction with the operation should be stopped at the latest by four weeks postoperatively. Patients using ARM after this period should actively be asked about this at the first follow-up (usually six weeks), and if no obvious reason exists it should be stopped. Similarly, if a patient is using ARM at the one-, two- or five year follow-up, the reason for this should be addressed.

Indications for reoperations due to GORD should be similar between institutions participating in this study. In general, patients having severe reflux symptoms despite high-dose ARM, and patients having endoscopically visible oesophagitis despite high-dose ARM could be considered for reoperation. Reoperations due to GORD are expected to be low during the first two years after the primary operation but possibly higher after five years.

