5.1.2 Primary and secondary endpoints

The primary endpoint is continuous use of ARM for GORD symptoms, or reoperation due to GORD within two years. This is easily measured and registered in most bariatric surgical

	RESEARCH PROTOCOL
Version no 4.0	Clinical intervention study

registries including SOReg. Daily use of ARM due to dyspepsia during the last month (as defined in SOReg) / reoperation due to GORD will be defined as "yes", otherwise "no".

Secondary endpoints are:

- a) PRO using the GerdQ and questionnaires for HRQL. GerdQ is a six item, easy to use questionnaire developed as a diagnostic tool for GORD.¹¹ It uses a four graded Likert scale (0-3), giving a total GerdQ score range of 0-18. Besides GerdQ, the questionnaires used for evaluating HRQL will be those that are already incorporated in the hospitals that will participate in the study. In Sweden this will be the SF-36, while in Norway only the initial question from SF-36 will be used together with PROSURG.¹²
- b) GORD as evaluated by endoscopy, pH-metry and impedance.

Endoscopy: Thirty patients will be submitted to a gastroscopy prior to, and two years after LSG/LSGG. A standard formula for evaluating and describing findings at gastroscopy will be used (appendix 1).

Reflux oesophagitis will be defined according to the Los Angeles classification (LA grade A-D), where grade C and D entails high-grade oesophagitis. ¹³ LA grade C and D, Barret's oesophagus and a peptic stricture will be considered confirmatory evidence of GORD.

pH-metry: GORD will be defined according to the oesophageal acid exposure time and the number of reflux episodes per 24 hrs. ¹⁴ pH-metry will only be performed in the subgroup of 30 patients before and two years after surgery using the Bravo-capsule. Patients having reflux symptoms responding to PPI but without acid reflux as evaluated by the Bravo capsule will be offered pH-impedance measurement.

c) Presence of a hiatal hernia as evaluated by endoscopy. The distance between the teeth and diaphragm, secondly the teeth and the GOJ will be measured and the difference calculated. If a part of the remaining stomach ascends into the thorax this will predispose to reflux as it is well known that a hiatal hernia (defined as ≥2 cm difference) is a predictor of reflux.¹⁵

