5.1.6 Including more subjects to compensate for drop-outs

If the recruitment of patients are lower than expected in Norway and Sweden, hospitals in other countries (primarily Netherland) will be invited to participate.

In order to reduce drop-outs, patients will be randomized in the operating room after being anesthetized and after the surgeon has decided to proceed with a LSG, but before surgery starts. Randomization will be performed by the use of sealed envelopes containing information on group allocation. Any patient who has signed for participation but are withdrawn before randomization will be replaced by one new subject. A list of patient(s) who withdraw after inclusion must be kept at the participating hospital and the reason for withdrawal must be stated. This list should be presented to SOReg-N on the first day of every month (see also 6.6.2).

Patients who withdraw or are withdrawn from the study after randomization cannot be replaced.

	RESEARCH PROTOCOL
Version no 4.0	Clinical intervention study

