7 STATISTICAL CONSIDERATIONS

7.1 Statistical design

Patients will be allocated in a 1:1 fashion between LSG and LSGG. Participating hospitals will administer this by block randomization with 10 patients (i.e. 5 LSG, 5 LSGG) in each block. Group allocation will be determined by opening of sealed envelopes. The envelopes will be distributed to participating hospitals from SOReg-N.

All patients will be given a unique patient number, and SOReg-N will be informed regularly about group allocation.

Analysis for outcome will be performed according to ITT. All patients will thus be analysed within the allocated group. Missing data at two and five years will be handled by multiple imputation. The main analysis for outcome will be based on logistic mixed effect models with odds ratio between groups corrected for age, smoking and surgeon. A sensitivity analysis including hospitals will also be performed.

Information on group allocation will be blinded to patients and researchers.

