7.8 Specification of subgroups

Gastroscopy and pH-metry of the distal oesophagus will be performed in a subgroup of 30 patients in hospitals where the Bravo capsule is available. Patients suspected of having non-acid reflux will be recommended pH- impedance measurements.

Patients having been reoperated due to reflux will be classified as failures and analyzed together with the ARM-group in their original cohort (LSG or LSGG), according to the ITT-principle.

Patients having been reoperated for other reasons (rare) will also be included in the ITT analysis.

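### Bravo hospitals must equalise pexy and no-pexy numbers themselves, but no concealed mechanism is given, so the 30-patient endoscopy/pH-metry comparison is open to site-controlled selection

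*Protocol*

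**What the plan says.** Only the protocol is at hand. The relevant statements are these.

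- **Balancing rule (section 6.6.2).** Bravo hospitals "must balance the number of patients themselves so that an equal number of patients are allocated to the pexy and no-pexy group, respectively". No method is given.
- **Who is in the subgroup (sections 5.1.2 and 7.8).** "Gastroscopy and pH-metry of the distal oesophagus will be performed in a subgroup of 30 patients in hospitals where the Bravo capsule is available". The capsule test is done at baseline and again at two years: "pH-metry will only be performed in the subgroup of 30 patients before and two years after surgery using the Bravo-capsule". Section 6.6.1 lists the baseline examination under screening, with tests generally allowed up to six months before the operation.
- **When the arm becomes known (section 5.1.6).** Every participant "will be randomized in the operating room after being anesthetized and after the surgeon has decided to proceed with a LSG, but before surgery starts".
- **How the arm is set (section 7.1).** The ratio is 1:1, and the method is blocking by hospital: "Participating hospitals will administer this by block randomization with 10 patients (i.e. 5 LSG, 5 LSGG) in each block". The supply is central: "The envelopes will be distributed to participating hospitals from SOReg-N". No stratum or separate series for Bravo patients is mentioned.
- **Who knows past allocations (sections 5.1.5 and 6.6.2).** The hospital's study coordinator keeps the list of who did and did not receive a pexy. The same coordinator's duties include recruitment.
- **Analysis (section 4).** Primary and secondary endpoints are analysed by intention to treat.

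**The concern.** Entry to the Bravo subgroup comes before the envelope is opened, so a hospital cannot know a patient's arm when it places the baseline capsule. Yet the hospital is made responsible for the arm totals coming out equal. A site that takes this literally, with only the tools in the protocol, has three obvious routes:

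1. offer the capsule to patients whose operation is expected to fall where the rest of a block favours the arm still short;
2. take an envelope out of order;
3. decide after allocation which capsule patients count or are brought back at two years.

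Each route lets a person's choice influence who is compared with whom. The planned pH-metry, and the endoscopic assessment of oesophagitis and hiatal hernia, rest on these 30 patients. With about 15 per arm, moving or losing a few selected patients could change the result. Acting on arm totals also means using unblinded information at the site, in a trial described as triple-blind. Analysis cannot restore concealment once it has been lost, so a statistical analysis plan could not repair this.

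**Working it through.** **Is there a plan figure to reproduce?** Not for this subgroup: the protocol states no sample size or power calculation for the 30. Its 686 and 858 concern the primary endpoint. They reproduce (14% v 7%, two-sided 5%, 85% power, pooled variance: 343 per arm, 686 in total; 686/0.80 = 857.5, rounded up to 858) and are not affected by this point.

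**Step 1. Would equal numbers arise without action by the site?** Inputs: 30 patients (section 7.8) and 1:1 allocation (section 7.1). The number and size of Bravo hospitals are not given, so the splits below are assumptions.

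| Assumption | Calculation | Chance of equality |
|---|---|---|
| Simple 1:1, 30 in total | C(30,15)/2^30 | 14.4% |
| 30 taken at random from 100 patients in one hospital, 50 per arm | C(50,15)²/C(100,30) | 17.2% |
| 3 hospitals × 10, each equal | (252/1024)³ | 1.5% |
| 5 hospitals × 6, each equal | (20/64)⁵ | 0.3% |

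The hospital blocks do not secure balance among Bravo patients, because these patients are only some of those in a block. Meeting the rule therefore usually requires the site to do something.

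**Step 2. Could a site act on the allocation?** Inputs: fixed blocks of 10 with 5 per arm (section 7.1), and past allocations known to the coordinator (section 5.1.5). I assume that the coordinator also knows the block size, which the protocol states openly.

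- Expected correct guesses per block, always guessing the arm with more places left: 5 + ½ × (2^10/C(10,5) − 1) = 5 + ½ × (1024/252 − 1) = 6.53 of 10, or 65% against 50% by chance.
- Expected number of allocations known with certainty at the end of a block: 10/(5 + 1) = 1.67 of 10.

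Timing a Bravo patient to the block remainder is thus feasible, though far from perfect.

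**Step 3. What does forced balance gain?** Under simple 1:1 allocation of 30:

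- P(split worse than 20:10) = P(X ≤ 9 or X ≥ 21), with X ~ Bin(30, 0.5), = 0.043.
- Variance of a difference at 20:10 relative to 15:15: (1/20 + 1/10)/(1/15 + 1/15) = 0.1500/0.1333 = 1.125, or 12.5% more.
- At 12:18: (1/12 + 1/18)/(2/15) = 0.1389/0.1333 = 1.042, or about 4% more.

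These figures use simple rather than blocked allocation. They measure only the precision lost to imbalance and say nothing about the size of any selection bias.

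**The case against.** The case on the other side is substantial.

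- **Balance can be reached without steering.** A reader might infer that equal numbers can be had only by manipulating allocation or selection. That is not so. A separate concealed series for Bravo patients would achieve it. So would taking every patient of complete blocks: three blocks of 10 give exactly 15:15. This stands. What remains is that the protocol provides neither and leaves the method to the hospital.
- **The protocol does not tell anyone to break randomization.** A reader might infer that randomization is already broken for these endpoints. The documents do not support that. Choosing envelopes would depart from sections 5.1.6 and 7.1, and section 10.1 requires adherence to the protocol. The text creates a risk and does not establish a breach.
- **Choice after allocation is constrained.** A patient cannot be added once the arm is seen unless a baseline capsule was already placed. Dropping one conflicts with intention to treat (section 4), and section 5.1.6 bars replacing patients withdrawn after randomization. This narrows the third route. It does not close it, because nothing says that Bravo membership is fixed at the baseline capsule, and the balancing rule pulls the other way.
- **Predictability is a wider problem.** The fixed blocks and the coordinator's double role concern all 900 patients and would exist without this sentence. That is true, but this sentence gives the site a reason to use what it knows.
- **The endpoints are secondary,** in 30 patients with no stated power. This bears on severity and is accepted.

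**Conclusion.** The point holds as a badly fixed rule: hospitals are made responsible for arm totals in the Bravo subgroup, with no concealed mechanism and with the allocation list in the recruiter's hands. It exposes the whole endoscopy/pH-metry comparison (30 patients, 15 per arm if equal) to selection bias. The size of that bias cannot be estimated from the documents.

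A reader might also infer that the primary result is compromised. It is affected only if envelope order is altered. The Bravo patients are 30/900 = 3.3% of the trial, but that is a head count and neither an estimate nor a bound on altered allocations.

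The conclusion assumes that no Bravo-specific envelope series exists outside the protocol and that sites know the block size. Severity: should fix.

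**What to change.** Either of two changes to section 6.6.2 would do.

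1. Delete the balancing sentence and accept the split that the main randomization gives. The cost is a possibly somewhat unequal split, with the small loss of precision shown above.
2. Replace the sentence with a separate concealed, blocked envelope series from SOReg-N for Bravo patients not yet randomized. The cost is one extra envelope pack per Bravo hospital. Bravo patients already randomized keep the allocation they have.

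In both cases, state that Bravo membership is fixed when the baseline capsule is placed, before the envelope is opened, and that all Bravo patients are analysed as randomized. It would also help to keep the allocation list away from whoever recruits.

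Either change is a protocol amendment, so under section 9 it needs agreement in the steering committee and ethics approval.
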